11.2. Adverse Event Documentation

Adverse events occurring from the first dose of 765IGF-MTX up to and including 30 days after administration of the last dose must be documented. Adverse events attributed to a study-related procedure which occur prior to the initiation of study treatment must be documented as well.

For the purposes of this study, adverse event documentation requirements will be determined based on grade, expectedness and relationship to study therapy as follows:

	Grade 1	Grade 2		Grade 3		Grade 4 and 5
	Expected or Unexpected	Expected	Un-expected	Expected	Un-expected	Expected or Unexpected
Unrelated	Not required	Not required	Not required	Not required	Required	Required

Possible						
Probable						
Definite	Not required	Required	Required	Required	Required	Required

All patients will be monitored with appropriate event documentation in EDC Easy® through the final study visit per section 7 as it is expected that most treatment related adverse events will occur during this period.

However, all toxicities (grades 1, 2, 3, 4, 5) must be reported within internal study forms, and include the following descriptors:

- Toxicity
- Grade
- Date
- Expected or Unexpected
- Attribution (unrelated, unlikely, possible, probably, definite)

For grade 2 or higher toxicities, principal investigator and/or treating physician will be notified the same day as study visit.

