3.1. Primary Endpoint

The primary endpoint is safety and tolerability of 765IGF-MTX. This will be assessed by evaluation of adverse effects (AEs) as defined by CTCAE v.4.0.

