12.1. Data Management

This study will report clinical data using the EDC Easy[®] Data Management System utilizing study specific case report forms. Key study personnel are trained on the use of case report forms and will comply with protocol specific instructions for data collection.

Patient demographics, patient specific study treatment calendars, adverse events and other information required for IND annual reporting will be maintained with EDC Easy[®].

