13.2.3. Safety Endpoints

Incidence rates of treatment-emergent adverse events will be summarized within treatment group at the MedDRA preferred term and primary system organ class levels. Similar summaries will be made for subsets of AEs such as (1) those judged by the Investigator to be related to study treatment, and (2) serious adverse events (SAEs). Other routine safety assessments (e.g., clinical laboratory parameters, ECG parameters, and vital signs) will be summarized by standard deviation, median, minimum and maximum observed values and changes from baseline values. NCI-CTCAE severity grades for laboratory parameters and other endpoints measured on an ordinal categorical scale may be summarized using shift tables (a two-way frequency table pairing baseline value with the most extreme post-baseline result).

Additional exploratory analyses may be performed to assist the sponsor in planning future studies.

13.3. Analysis plan for primary objective:

The primary objective is to determine safety and tolerability of 765IGF-MTX by evaluation of toxicity for the treatment of advanced, previously treated hematologic malignancies. Preliminary information will be collected for treatment related toxicity and tolerance. Toxicity will be graded using the NCI's Common Terminology Criteria for Adverse Events version 4 (CTCAE v.4.0). Treatment tolerance will be based on the number of dose-limiting toxicities, treatment delays and dose reductions. Information will be presented in a tabular and descriptive manner.

13.4 Analysis plan for secondary objectives:

13.4.1 Objective Response Rate, Relapse-Free Survival, Overall Survival and Cumulative Incidence of Relapse; descriptive statistics will be used to describe clinical benefit measured by the above parameters.

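### Section 11.2 exempts some adverse events from documentation by grade, expectedness and attribution, and does not link its all-grade internal forms to the database behind the unfiltered AE tables in Section 13.2.3

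*Combined protocol and SAP*

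**What the plan says.** Section 11.2 opens with an unrestricted rule: "Adverse events occurring from the first dose of 765IGF-MTX up to and including 30 days after administration of the last dose must be documented". It then narrows the rule: "adverse event documentation requirements will be determined based on grade, expectedness and relationship to study therapy as follows". The unrelated row of the matrix reads "Unrelated Not required Not required Not required Not required Required Required" and the last row of the related block reads "Definite Not required Required Required Required Required Required". The columns are grade 1; grade 2 expected and unexpected; grade 3 expected and unexpected; and grades 4 and 5 together.

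The next sentence refers to appropriate event documentation in EDC Easy. The section continues: "However, all toxicities (grades 1, 2, 3, 4, 5) must be reported within internal study forms". The descriptors for those forms are toxicity, grade, date, expectedness and a five-level attribution that includes unrelated and unlikely.

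On where data are held, Section 12.1 begins "This study will report clinical data using the EDC Easy" (the system's full name follows) and says that adverse events are maintained there. Section 12.2 calls the data collection forms CRFs.

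On the analysis, Section 3.1 says of the primary endpoint, safety and tolerability: "This will be assessed by evaluation of adverse effects (AEs) as defined by CTCAE v.4.0". Section 13.2.3 plans that "Incidence rates of treatment-emergent adverse events will be summarized within treatment group at the MedDRA preferred term" and system organ class, and lists related AEs and SAEs as subsets with similar summaries.

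**The concern.** The main table in Section 13.2.3 has no grade or attribution limit. Because related events are a subset of it, it must be an all-cause table. The matrix in Section 11.2 does not require all the events that such a table needs.

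The trial has no control arm. Section 1.2.1 says cytopenia is a principal sequela of the diseases under study, so drug effects and disease effects are hard to separate for an individual patient. An all-cause table is useful here because it lets a reader look past the investigator's causal judgement. If attribution decides which events reach the database, the table can no longer serve as that check. A drug effect misjudged as unrelated at grade 2 would be missing from both the related table and the all-cause table. Low-grade events count too: Section 7.2.1, for example, describes grade 1 hypersensitivity as its own category.

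**Working it through.** The plan gives no figure to reproduce and no AE rates, so the check compares passages.

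**Step 1. Read the matrix (Section 11.2).**

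| | Gr 1 | Gr 2 expected | Gr 2 unexpected | Gr 3 expected | Gr 3 unexpected | Gr 4-5 |
|---|---|---|---|---|---|---|
| Unrelated | no | no | no | no | yes | yes |
| Possible, probable or definite | no | yes | yes | yes | yes | yes |

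Here *no* means that documentation is not required. That is 4 of 6 columns for unrelated events and 1 of 6 for related events. The matrix was read from a PDF, so I draw nothing from its blank cells or from the absence of an *unlikely* row.

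**Step 2. Do not treat the cell count as a size.** As printed, 4 + 1 = 5 of 12 cells are not required. Unfolded to 5 grades × 2 expectedness × 2 relationship = 20 cells, the count is 5 unrelated (grade 1 twice, grade 2 twice, expected grade 3 once) plus 2 related (grade 1 twice) = 7 of 20. The fraction depends on the layout, and neither version measures events.

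**Step 3. Remove what reaches the database by another route.** Section 11.4 requires all SAEs regardless of expectedness or relationship, entered in the SAE section of EDC Easy. The gap is therefore confined to non-serious events. Section 11.1 classes disease-process events as unexpected, so a grade 3 event caused by the disease falls in a required cell and the grade 3 gap is narrow.

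**Step 4. State what the tables would contain if EDC Easy held only required events.**
- All-cause table: no non-serious grade 1 events, no non-serious unrelated grade 2 events, and no non-serious unrelated expected grade 3 events.
- Related table: no non-serious grade 1 events.
- The two tables could differ only through SAEs, unrelated unexpected grade 3 events and unrelated grade 4-5 events. Non-serious grade 2 events would add nothing to the difference.

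**Step 5. Check the dose-finding rules (Section 4).** The trigger for cohorts of 3 is a related event of grade 2 or higher, with some exceptions. Two DLT criteria rest on related toxicity at grade 3 or 4 and above. The matrix requires all of these. Febrile neutropenia, and platelets below 10 × 10⁹/L with clinically significant bleeding, count as DLTs without a relatedness condition. Such an event would be exempt only if non-serious, judged unrelated, and either below grade 3 or an expected grade 3 event. Step 3 makes that a narrow case, and I do not rest the point on it.

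**Step 6. Scale.** For one preferred term, incidence from the database is (A − E)/N. A is the number of patients with the event, and E is the number whose only occurrences were not entered. E is unknown. With N = 9 (the MTD cohort), each such patient lowers incidence by 1/9 = 11.1 percentage points. With the largest total that the dose-level table allows, 5 × 9 = 45, it is 1/45 = 2.2 points. These are step sizes, not estimates of the loss.

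**The case against.** The strongest reply is that the data are to be collected. The internal forms carry all five grades with attribution, the opening sentence of Section 11.2 has no limit, and Section 12.1 puts adverse events in EDC Easy without a grade restriction. Nothing says that the internal forms stay outside the database. This stands against one tempting inference, that these events are irretrievably lost or that the all-cause tables must be incomplete. The documents support only the conditional statement. It does not remove the problem. The forms are mentioned once, are undefined, and are introduced in contrast to the sentence on EDC Easy; a site that follows the matrix as written would be compliant and would leave these events out.

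A reader might also infer that the primary safety result is biased downward. That is not shown. Section 13.3 analyses the primary objective through treatment-related toxicity, DLTs, treatment delays and dose reductions, which the matrix leaves largely intact. Blood counts and chemistry are scheduled in Section 8.1 regardless of attribution and are summarized under Section 13.2.3, so laboratory abnormalities have a separate route. Symptoms reported by patients do not have that route.

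Nor is the all-cause grade 2 table identical to the related one by construction. Unrelated grade 2 SAEs are captured, and Section 13.2.3 specifies no table by grade.

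Finally, Section 13 calls itself an overview, with a full SAP to follow before database lock. That SAP could name the data source, but it cannot tabulate events that were never entered.

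**Conclusion.** The point holds as a conflict between the capture rule and the planned analysis. Section 11.2 does not require some events that the tables in Section 13.2.3 need, and the forms that would fill the gap are not linked to the analysis data. The consequence rests on one assumption that the documents leave open: that EDC Easy holds only what the matrix requires. Under it, the all-cause tables are filtered in part by investigator attribution before analysis, and the related table has no non-serious grade 1 events. The gap is clear at grades 1 and 2 and narrow at grade 3. SAEs, grade 4-5 events, related events of grade 2 or higher and the related-toxicity DLTs are not affected. The number of events or patients missed cannot be derived from the documents, and any assumed share of unrelated events would not convert directly into lost incidence, since a patient with another recorded event of the same term is still counted. The events remain recoverable if the internal forms are complete. The change should be made, because the conflict falls on the safety tables of a trial whose primary endpoint is safety.

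**What to change.** In Section 11.2, require every AE of any grade, expectedness and attribution, from first dose to 30 days after the last dose, to be entered in EDC Easy with the descriptors already listed for the internal forms. Delete the matrix as a limit on data capture. Do not reuse it for expedited reporting: Section 11.3 already sets those criteria on a different basis. State in Section 13.2.3, and in the full SAP, that the all-cause and related tables are built from this complete set.

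The cost is extra data entry for at most 45 patients (5 dose levels × 9). No new assessments are needed, because the items are already to be recorded on the internal forms.

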11.3 Required Reporting, IRB, FDA, IGF Oncology, LLC

Agency	Criteria for reporting	Timeframe	Form to Use	Submission address/ fax numbers	Copy AE to:
Study Site IRB	UPIRSO: Events which are unanticipated, involved risk to subjects or others, and was at least possibly related to study procedures/treatment	5 Working Days	EDC Easy® (Paper report can be generated from system)/ Mayo Clinic IRB Prompt Report Form	Study Site IRB	Study Site Regulatory Coordinator
	Other Problems or Events meeting the definition of UPIRSO in section 11.1	5-15 Working Days per IRB requirements	Mayo Clinic Rochester IRB/Prompt Report Form		
FDA	Unexpected and fatal or life threatening suspected adverse reaction	As soon as possible but no later than 7 Calendar Days	Medwatch/ EDC Easy® (Paper report can be generated)	Fax SAE to IND/IDE Regulatory Health Project Manager, [name], R.N., B.S.N., Division of Oncology Products 1 at [name].	

FDA (continued)	1) Serious and unexpected suspected adverse reaction or 2) increased occurrence of serious suspected adverse reactions over that listed in the protocol or investigator brochure or 3) findings from other sources (other studies, animal or in vitro testing)	As soon as possible but no later than 15 Calendar Days	from system)	Email: [contact] Follow-up with written report submitted as an amendment to: MedWatch, [name]	
		All other events per CRF 312.33	At time of IND annual report	Summary format	Submit as part of the IND annual report

Note: Events due to the disease under treatment or an underlying medical condition will not require expedited reporting to the FDA for the purposes of this study

IGF- Oncology, LLC	All serious adverse events, regardless of expectedness or relationship with any study drug per section 11.4	Within 24 hours of knowledge	SAE Initial and Follow-up Report Forms provided to each site	IGF Clinical Operations Team (SAE and Pregnancy Reporting Contact Information): [name]., IGF Oncology, President, CEO [contact] [contact]

Investigator must report all SAEs, regardless of expectedness or relationship with any study drug, to the IGF Oncology Clinical Operations team (contacts noted in above chart) as soon as possible, but no later than 5 calendar days of the sponsor-investigator's observation or awareness of the event. In the event that this is a multisite study, the sponsor-investigator is responsible to ensure that the SAE reports are sent to the IGF Oncology Clinical Operations team (contacts noted on page 42) and reports will be sent to all sites participating in the study. Subinvestigators must report all SAEs to the sponsor-investigator so that the sponsor-investigator can meet his/her foregoing reporting obligations to the IGF Oncology Clinical Operations team, unless otherwise agreed between the sponsor-investigator and subinvestigator(s). The IGF Oncology Clinical Operations team may request follow-up information to a reported SAE, which the sponsor-investigator will be responsible for providing to the IGF Oncology Clinical Operations team.

The SAE report must include event term(s), serious criteria, and the investigator's or sub-investigator's determination of both the intensity of the event(s) and the relationship of the event(s) to study drug administration.

Intensity for each SAE, including any lab abnormality, will be determined by using the NCI CTCAE v.4.0.

Relationship to all study drugs for each SAE will be determined by the investigator or sub-investigator by responding yes or no to the question: Is there a reasonable possibility that the AE is associated with the study drug.

Sponsor-investigator must also provide the IGF Oncology Clinical Operations team with a copy of all communications with applicable regulatory authorities related to the study or study

drug(s), including, but not limited to, telephone conversation logs, as soon as possible but no later than 5 calendar days of such communication.

Data will be entered in the SAE section of EDC Easy[®], from which a paper report can be generated at any time. In addition, IGF Oncology will provide the investigators with both an Initial SAE Report Form, (to be completed at the time of the SAE) and an SAE Follow-up Report form (to be completed when all follow-up information has been gathered). The SAE Report forms should be E-mailed to the IGF Oncology Clinical Operations team (contact E-mails are noted on the chart above (page 42).

11.5 Procedures for Reporting During Pregnancy and Birth Events

If a woman becomes pregnant or suspects that she is pregnant while participating in this study, she must inform the investigator immediately and must permanently discontinue study drug(s). All pregnancies and suspected pregnancies must be reported to the IGF Oncology Clinical Operations team immediately using a Pregnancy Report Form (see Section 11.3 for contact information). The pregnancy must be followed for the final pregnancy outcome (i.e., delivery, still birth, miscarriage) and the IGF Oncology Operations team will request this information from the investigator.

If a female partner of a male patient becomes pregnant during the male patient's participation in this study, this must be reported to the IGF Oncology Clinical Operations team immediately using a Pregnancy Report Form (see Section 11.3 for contact information). Every effort should be made to follow the pregnancy for the final pregnancy outcome.

12. Study Data Collection and Monitoring

12.1. Data Management

This study will report clinical data using the EDC Easy[®] Data Management System utilizing study specific case report forms. Key study personnel are trained on the use of case report forms and will comply with protocol specific instructions for data collection.

Patient demographics, patient specific study treatment calendars, adverse events and other information required for IND annual reporting will be maintained with EDC Easy[®].

12.2. Case Report Forms

Participant data will be collected using protocol specific case report forms (CRFs). The CRFs will be approved by the study's Principal Investigator and the study biostatistician prior to release for use. The Study Coordinator or designee will be responsible for registering the patient into EDC Easy[®] at time of study entry, completing CRFs based on the patient specific calendar, and updating the patient record until patient death or end of required study participation.

12.3. Data and Safety Monitoring Plan (DSMP)

The study's Data and Safety Monitoring Plan will be in compliance with Mayo Clinic Cancer Center's Data & Safety Monitoring Plan (DSMP).

For the purposes of data and safety monitoring, this study is classified as high risk (under a locally held IND). Therefore, the following requirements will be fulfilled:

- The PI will complete and submit a quarterly Trial Progress Report to the Cancer Center Data and Safety Monitoring Committee (DSMC) with the understanding the Cancer Center Protocol Review Committee (CCPRC) may require more frequent reporting.

- The PI will comply with at least twice yearly monitoring of the project by the Cancer Center monitoring services.
- The PI will oversee the submission of all reportable adverse events per the definition of reportable in section 11.3 to the Cancer Center's SAE Coordinator, the Mayo Clinic IRB, and the FDA.

In addition, at the time of the continuing review with the Mayo Clinic IRB, a copy of the report with any attachments will be submitted to the Protocol Review Committee (PRC).

IND Annual Reports

In accordance with regulation 21 CFR § 312.33, the sponsor will submit a progress report annually. The report will be submitted within 60 days of the anniversary date that the IND went into effect. Included as a part of the annual report for this IND will be initial reporting of all deaths due to disease at any time and all deaths (regardless of cause) occurring more than 2 years after 765IGF-MTX infusion.

12.4. Monitoring

The investigator will permit study-related monitoring, audits, and inspections by the study's Investigator and/or any designees, the local IRB, government regulatory bodies, and Mayo Clinic compliance groups. The investigator will make available all study related documents (e.g. source documents, regulatory documents, data collection instruments, study data, etc.). The investigator will ensure the capability for inspections of applicable study-related facilities (e.g. pharmacy, diagnostic laboratory, etc.) will be available for trial related monitoring, audits, or regulatory inspections.

12.5. Record Retention

The investigator will retain study records including source data, copies of case report form, consent forms, HIPAA authorizations, and all study correspondence in a secured facility for at least 6 years after the study file is closed with the IRB and FDA.

In addition, the CTO will keep a master log of all patients participating in the study with sufficient information to allow retrieval of the medical records for that patient.

The CTO must be contacted before destroying any study related records.

13. Statistical Considerations

A brief overview of the statistical analysis plan is presented below. Complete details of the planned analysis will be documented in a full Statistical Analysis Plan, which will be finalized before locking the study database.

13.1. Sample Size

Given the design and primary objectives of this study, the sample size will be determined by the guidelines governing dose escalation/de-escalation and the identification of DLTs. As a result, the final sample size is not fixed and will not be determined by consideration of inferential analyses conducted via statistical hypothesis testing.

13.2. Statistical Methods

Statistical analyses will be performed using SAS software version 9.4 or higher. In general, data summaries will be compiled by 765IGF-MTX dose level and overall and will include the mean,

standard deviation, median, minimum and maximum values for continuous data; the median, 25th and 75th percentiles, minimum and maximum values for time-to-event endpoints; and the number and percentage of patients in each category for categorical data. Pointwise 95% confidence intervals (CI) will also be estimated for the mean (continuous data), median (time-to-event endpoints) or percentage of patients (categorical data).

Baseline value of a characteristic is defined as the last measured value prior to the first dose of 765IGF-MTX.

Descriptive statistics such as Spearman or Pearson correlation coefficients will be estimated with 95% CIs to assess the relationship between anti-765IGF antibody and anti-765IGF-MTX antibody levels with clinical response and toxicity.

13.2.1. Efficacy Endpoints

The numbers of overall complete remissions (patients with a best objective response of CR or CRi), and overall remissions (patients with a best objective response of CR, CRi or PR) will be summarized by observed rates and estimated 95% CIs. If there are sufficient numbers of patients achieving remissions for an analysis to be informative, logistic regression will be used to model the probability of achieving a remission as a function of the assigned 765IGF-MTX dose level for Cycle 1. Other factors may be added to the model to investigate their prognostic value in predicting remission.

In general, missing values will not be replaced by imputed values. Patients who, for any reason, do not supply bone marrow for response assessment are counted among those not achieving a response.

Kaplan-Meier time-to-event analyses will be conducted on overall survival and progression-free survival. Mortality (all causes) at certain landmark time points (e.g., 90 and 180 days) will also be estimated together with 95% CIs. Cox proportional hazards models will be fit to these time-to-event endpoints with the assigned 765IGF-MTX dose level for Cycle 1 serving as the independent variable in the model.

